#### 2. Adjustment of Study Visits

Telemedicine is understood as a possible solution due to COVID-19 disruption and it is not mandatory; if the situation allows it, study visits should be done in person.

**On-site Study Visit:** If the local situation allows for conduct of on-site study visits, the PI and study personnel must take all necessary steps/precautionary measures at the site to minimize or eliminate immediate hazards of viral transmission within and/or outside the clinical site premises.

Before any research activities occur on-site, both subjects and research staff should be screened for symptoms or risk of COVID-19 infection. Subjects should be pre-screened by phone before their on-site study visit.

If the local situation only allows for completion of some study procedures, the PI will prioritize the research activities that absolutely require an in-person visit in order to maintain the viability and integrity of the research (e.g., Treatment Visit). The PI may consider conducting the other assessments (e.g., medical history review, directed questionnaire) using telemedicine to minimize subject time on site and risk of exposure at the site. However, all efforts should be made to conduct all assessments at the scheduled visits, if possible.

**Remote Study Visit:** If the local situation does not allow for an on-site study visit to be conducted or if a subject does not wish to come to the study site due to COVID-19 disruption, a remote study visit may be conducted via video conferencing in lieu of an on-site visit. Phone call may also be used to perform some assessments if a subject has no video conferencing capabilities.

The PI or study personnel who will conduct remote visits must be trained on how to conduct realtime video conferencing visits. Also, procedures should be put in place to maintain the subject's privacy, as would be done for a clinical visit:

#### • Before the scheduled date of the visit:

- The site personnel should determine if the subject can accommodate for video conferencing (e.g., internet access, PC, smartphone, video conference apps, etc.).
- The PI or site personnel conducting the remote visit should obtain the subject's verbal consent before proceeding with the visit and document it in the source document. The PI or personnel should also explain to the subject how the visit will be conducted.
- A test call may also be completed with the subject prior to the appointment.
- On the day of the scheduled visit:
  - Both the investigator/site delegate and the subject should confirm their respective identities with one another before engaging in a real-time video conference visit. For example, the site personnel will state their name and role and the subject may be identified by using two subject identifiers (e.g., name and date of birth) and a photo ID.
  - The date and time of the real-time video interaction, the location of the subject, and the location of the PI or site personnel conducting the remote visit should be documented in the source document.
  - Remote collection of data by PI or delegate will be conducted as described in Section 3 below.

#### 3. Adjustment of Study Assessments

**Informed consent:** The following process will be followed for consenting a prospective subject remotely:

- Each subject will be provided with a copy of the IRB-approved consent form to aid in the consent discussion before the consent process begins. The consent form may be provided to a prospective subject by mail or e-mail.
- The PI and/or site delegate will participate in the consent process via video conference. All parties must introduce themselves and their role in the consenting process.
- The consent form provided to the subject will be reviewed in detail and the subject will be invited to ask any questions and to have them addressed by the study team.
- If the subject is interested in joining the research study, the subject will be asked to sign the consent document. The personnel conducting the consent process must verify that the

subject physically signed the consent document by viewing via video conference and then obtain a photo or scanned copy of the signed consent form before proceeding with study assessments.

- In order to obtain the required signatures from the PI and person conducting the consent process on the same day, the site will either sign a separate copy of the informed consent form or ask the subject to send a copy of the signed ICF by e-mail.
- The site should ensure to obtain all signature pages from the subject and to document the consent process in the source document. The site should also file in the source document all signed components as one combined document and provide a copy to the subject.

**Inclusion/Exclusion Criteria:** The list of inclusion/exclusion criteria may be reviewed via video conference or phone call with the subject to confirm that they are eligible for the study.

For potential subjects in a high-risk population for COVID-19 (e.g., 60 years old and older, with comorbidities such as diabetes, cardiovascular disease, respiratory system issues, etc.), deferring participation should be considered to minimize risks of exposure.

**UPT (if applicable):** UPTs cannot be conducted remotely.

**Demographics:** Demographic information may be collected via video conference or phone call from the subject at a remote screening visit.

**Medical History and Concomitant Medications:** Medical history and concomitant medications may be reviewed via video conference or phone call at each remote visit.

**Randomization:** Randomization is performed before treatment. Therefore, subjects will be required to present themselves at the clinic for randomization.

**IP Treatment Session:** IP cannot be administered remotely. Therefore, subjects will be required to present themselves at the clinic for the IP treatment session.

Vital Signs, Physical Exam, Safety Laboratories, ECG: Subjects will be required to present themselves at the clinic for assessment of vital signs, physical examinations, clinical labs, and ECGs.

**Brow Area Photography:** Subjects will be required to present themselves at the clinic for photography sessions of the brow area.

**Directed Review of Systems:** Subjects will be required to present themselves at the clinic for the directed review of systems.

Adverse Events: AEs may be reviewed remotely via video conference or phone call with the subject at each remote study visit. Any AE/SAE (including suspected / confirmed COVID-19 cases) elicited by a subject during a remote visit / phone call must be immediately captured, and all attempts should be done to capture the necessary clinical and medical information. Reporting of AEs and SAEs to the Sponsor and IRB should follow the protocol procedure and IRB requirements.

**Investigator Assessments (GLS, GAIS):** The primary effectiveness endpoint will be based on the GLS as assessed by the Investigator. As such, the Investigator assessment of the GLS cannot be conducted remotely and subjects will be asked to travel to the clinic in order for the Investigator to perform a live GLS assessment. If this is impossible, GLS may be conducted remotely via video

$\mathfrak{B}$	evo	US™
----------------	-----	-----

conference; however, such data collected will not be part of the primary effectiveness endpoint analysis and will be used as supportive data only. The GAIS may be conducted remotely via video conference or phone call with the subject.

Subject Assessments (GLS, GAIS, Subject Satisfaction, Clinical Interview, Directed Questionnaire): All subject assessments may be conducted remotely via video conference or phone call with the subject at each remote visit. Subjects will be interviewed by the study coordinator who will record responses into the source document worksheets. In order to perform the GAIS, the subject's Baseline photo will also be provided by email.

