#### 10.3.2 Global Aesthetic Improvement Scale (GAIS)

GAIS will be assessed by both the Investigator (Blinded Evaluator) and subjects using the 5-grade scale as per Table 3 below. Instruction for assessment: "Compare your pre-injection photograph to the photograph provided and rate the degree of aesthetic improvement by using the following scale". Investigator and subject will assess using the same pre-injection photograph.

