7.2. Secondary Effectiveness Endpoints

Secondary effectiveness endpoints will be used to provide additional analyses regarding duration of effect of prabotulinumtoxinA 40U, prabotulinumtoxinA 20U, and onabotulinumtoxinA 20U. As duration of effect outcomes, secondary effectiveness endpoints will be assessed as described above for the primary endpoint. The mITT population will be used for summaries and comparisons. Secondary endpoints, in order of importance, will be:

- 1. Duration of effect (PraB vs. OnaB only, regardless of responder status), defined as the number of days from Treatment Day (Baseline) to the day that GLS severity (Investigator assessment) at maximum frown returns to the Baseline value.
- 2. Duration of effect (all treatment groups, regardless of responder status), defined as the number of days from Treatment Day (Baseline) to the day that GLS severity (subject assessment) at maximum frown returns to the Baseline value.
- 3. Duration of effect (all treatment groups) in GAIS responders (score of 2 or 1 at Day 30) as assessed by Investigator.
- 4. Duration of effect (all treatment groups) in GAIS responders (score of 2 or 1 at Day 30) as assessed by subject.
- 5. Duration of effect (all treatment groups) in SSS responders (score of 2 or 1 at Day 30) as assessed by subjects.

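### Appendix A lets the Investigator score GAIS by telephone, with no view of the face and no current study photograph, and no rule keeps that score out of the Investigator GAIS endpoints

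*Protocol*

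**What the plan says.** Protocol Appendix A, section 3, deals with the two Investigator ratings in one paragraph. Investigator GLS is to be scored live. If that is impossible it may be done by video, in which case "such data collected will not be part of the primary effectiveness endpoint analysis and will be used as supportive data only". The next sentence reads: "The GAIS may be conducted remotely via video conference or phone call with the subject". It attaches no limit on how the score may be used.

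Subject-rated scales, GAIS among them, have a separate paragraph: "All subject assessments may be conducted remotely via video conference or phone call with the subject at each remote visit". Appendix A, section 2, makes video the normal form of a remote visit and adds: "Phone call may also be used to perform some assessments if a subject has no video conferencing capabilities".

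Protocol 10.3.2 has the Investigator and the subject both score GAIS on this instruction: "Compare your pre-injection photograph to the photograph provided and rate the degree of aesthetic improvement by using the following scale". For photography, Appendix A says: "Subjects will be required to present themselves at the clinic for photography sessions of the brow area".

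In the SAP, 7.2 item 3 is duration of effect "in GAIS responders (score of 2 or 1 at Day 30) as assessed by Investigator", and 7.3 item 5 is the GAIS response rate at each visit, by Investigator and by subject. In the protocol, Investigator GAIS duration is secondary endpoint 2 (12.2) and tertiary endpoint 3 (12.3).

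**The concern.** GAIS is a visual rating. On a telephone call the Investigator cannot see the subject and has no photograph from that visit, so there is nothing current to compare with the pre-injection image. A number recorded as an Investigator assessment would not be an Investigator observation.

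Two things are at stake. First, Investigator GAIS and subject GAIS are listed as separate secondary endpoints, and agreement between them is informative only if the Investigator has judged independently. Second, GAIS supplies both the responder definition and the event for the duration endpoint, since Table 14.3.2.3 counts return to the Baseline GAIS score. A telephone score can therefore affect who is analysed and when the event is recorded.

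**Working it through.** The plan has no figure to reproduce here. The check sets the relevant texts side by side.

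1. *Whose rating does the sentence cover?* It stands in the paragraph on Investigator assessments, and subject GAIS has its own remote rule in the paragraph that follows. Read as applying to the subject only, the sentence would be redundant. It covers the Investigator's score.

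2. *What can the Investigator see?* From Protocol 10.3.2 and Appendix A, section 3:

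| Mode | View of the face | Study photograph from that visit | Allowed for Investigator GLS | Allowed for Investigator GAIS |
|---|---|---|---|---|
| Clinic | yes | yes | yes | yes |
| Video | yes, on screen | no | yes, but outside the primary analysis | yes, no limit on use |
| Telephone | no | no | no | yes, no limit on use |

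The defect is the last row. The only image Appendix A supplies for a remote GAIS is the Baseline photograph emailed to the subject.

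3. *Where does the score go?* SAP 7.2 uses the mITT population. Membership (SAP 7.5.1) depends on randomization, injection and one post-dosing assessment of the primary endpoint, not on how GAIS was obtained. SAP 7.3 item 5 uses observed GAIS scores without imputation (SAP 7.7). Neither section mentions assessment mode.

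4. *Does another provision remove it?*
   - Appendix A, section 1, has COVID-19 deviations, remote visits included, annotated as such. That makes them traceable but does not exclude them.
   - The PP population (SAP 7.5.2) drops deviations that could affect effectiveness assessments, but it is supportive only.
   - Protocol 12.8 foresees post-hoc COVID-19 sensitivity analyses where warranted. That is not a pre-specified exclusion, and SAP 7.7 does not repeat it.

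5. *How many scores?* The documents give no number of remote or telephone visits. Let p be the share of Day 30 visits held remotely and f the fraction of those without video. The expected number of telephone-only Day 30 scores per arm is 50 × p × f, which cannot exceed 50 × p because f ≤ 1. With p assumed to be 2% to 10%:
   - 50 × 0.02 = 1
   - 50 × 0.10 = 5

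   So 1 to 5 per arm is the ceiling under that assumption, reached only if no remote subject had video. It refers to one visit. The number of subjects with a telephone score at any later visit is equally unknown.

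**The case against.** The strongest reply is that this is a narrow contingency. In-person visits are preferred, video comes next, sites check video capability beforehand, and subjects are asked to travel to the clinic for the Investigator GLS due at the same visits. Telephone-only Investigator GAIS should be rare. That stands, and it limits the size of the point.

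GLS carries the primary endpoint and GAIS does not, so a looser rule for GAIS may be a deliberate ranking. That can explain why remote GAIS is not held to the GLS rule. It does not explain accepting a visual rating made without seeing anything.

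The protocol and SAP also describe their analyses as for interpretation only (Protocol 1.3, SAP 1.3), which limits the consequences further.

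Four stronger readings are tempting, and the documents do not support them:

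- *That 1 to 5 subjects per arm would be rated unseen.* That counts every remote visit. A subject on video is seen.
- *That the plan already voids remote Investigator GLS, so GAIS should simply match.* The GLS limit is worded for the primary analysis. It does not set values to missing or bar them from exploratory endpoints, and nothing in it calls for discarding video GAIS.
- *That a telephone score at Day 30 decides responder status.* SAP 7.2 defines response at Day 30, but the footnote to Table 14.3.2.3 accepts a response by Visit 5 or earlier. Under the footnote a 48-hour in-clinic score could already qualify the subject.
- *That a telephone score is necessarily a copy of the subject's own score.* The documents name no other current source for it, but they do not say how the Investigator would arrive at it.

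The missing-photograph argument also touches remote subject GAIS. There, however, the subject can see their own face and has the Baseline photograph, so the case for changing that rule is much weaker.

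**Conclusion.** The point holds, at low severity. Followed as written, Appendix A allows an Investigator GAIS score given with no view of the face and no current study photograph. No text excludes that score from SAP 7.2 item 3 or SAP 7.3 item 5. The existing safeguards make such visits traceable but leave the scores in the mITT analysis.

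This conclusion rests on the wording alone. Its practical size is unknown: possibly zero, and at Day 30 no more than 1 to 5 of 50 per arm if 2% to 10% of visits were remote. The primary endpoint is not affected, and nothing here counts against video ratings or subject-rated GAIS.

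**What to change.** Two sentences.

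- *Protocol Appendix A, section 3:* in the sentence on GAIS in the Investigator paragraph, delete the telephone option. Leave video, and the paragraph on subject assessments, as they are.
- *SAP 7.7, Missing Values:* add that an Investigator GAIS score obtained by telephone only is treated as a missing assessment in 7.2 item 3 and 7.3 item 5, and that the remote visit still counts as attended. The second half is needed because SAP 7.7 treats failure to attend two consecutive visits as return to Baseline. A voided score at an attended visit should not trigger that rule.

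The SAP sentence also covers telephone scores already collected, provided it is in place before database lock.

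The cost is a few missing Investigator GAIS values. For the duration endpoint, status at such a visit is unobserved. A subject whose Day 30 value becomes missing may leave the Investigator GAIS responder subset, unless an earlier in-clinic response counts under the footnote to Table 14.3.2.3. SAP 7.2 and that footnote should be made to agree, so that the handling of these subjects is fixed in advance.

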## **APPENDIX B: DECLARATION OF HELSINKI**

# WORLD MEDICAL ASSOCIATION DECLARATION OF HELSINKI Ethical Principles for Medical Research Involving Human Subjects

Adopted by the 18th WMA General Assembly, Helsinki, Finland, June 1964, and amended by the: 29th WMA General Assembly, Tokyo, Japan, October 1975 35th WMA General Assembly, Venice, Italy, October 1983 41st WMA General Assembly, Hong Kong, September 1989 48th WMA General Assembly, Somerset West, Republic of South Africa, October 1996 52nd WMA General Assembly, Edinburgh, Scotland, October 2000 53rd WMA General Assembly, Washington 2002 (Note of Clarification on paragraph 29 added) 55th WMA General Assembly, Tokyo 2004 (Note of Clarification on Paragraph 30 added) 59th WMA General Assembly, Seoul, October 2008

#### A. INTRODUCTION

- 1. The World Medical Association has developed the Declaration of Helsinki as a statement of ethical principles to provide guidance to physicians and other participants in medical research involving human subjects. Medical research involving human subjects includes research on identifiable human material or identifiable data.
- 2. It is the duty of the physician to promote and safeguard the health of the people. The physician's knowledge and conscience are dedicated to the fulfillment of this duty.
- 3. The Declaration of Geneva of the World Medical Association binds the physician with the words, "The health of my patient will be my first consideration," and the International Code of Medical Ethics declares that, "A physician shall act only in the patient's interest when providing medical care which might have the effect of weakening the physical and mental condition of the patient."
- 4. Medical progress is based on research which ultimately must rest in part on experimentation involving human subjects.
- 5. In medical research on human subjects, considerations related to the well-being of the human subject should take precedence over the interests of science and society.
- 6. The primary purpose of medical research involving human subjects is to improve prophylactic, diagnostic and therapeutic procedures and the understanding of the aetiology and pathogenesis of disease. Even the best proven prophylactic, diagnostic, and therapeutic methods must continuously be challenged through research for their effectiveness, efficiency, accessibility, and quality.
- 7. In current medical practice and in medical research, most prophylactic, diagnostic and therapeutic procedures involve risks and burdens.
- 8. Medical research is subject to ethical standards that promote respect for all human beings and protect their health and rights. Some research populations are vulnerable and need special protection. The particular needs of the economically and medically disadvantaged must be recognized. Special attention is also required for those who cannot give or refuse consent for themselves, for those who may be subject to giving consent under duress, for those who will not benefit personally from the research and for those for whom the research is combined with care.
- 9. Research Investigators should be aware of the ethical, legal and regulatory requirements for research on human subjects in their own countries as well as applicable international requirements. No national ethical, legal or regulatory requirement should be allowed to reduce or eliminate any of the protections for human subjects set forth in this Declaration.

#### **B. BASIC PRINCIPLES FOR ALL MEDICAL RESEARCH**

- 10. It is the duty of the physician in medical research to protect the life, health, privacy, and dignity of the human subject.
- 11. Medical research involving human subjects must conform to generally accepted scientific principles, be based on a thorough knowledge of the scientific literature, other relevant sources of information, and on adequate laboratory and, where appropriate, animal experimentation.
- 12. Appropriate caution must be exercised in the conduct of research which may affect the environment, and the welfare of animals used for research must be respected.
- 13. The design and performance of each experimental procedure involving human subjects should be clearly formulated in an experimental protocol. This protocol should be submitted for consideration, comment, guidance, and where appropriate, approval to a specially appointed ethical review committee, which must be independent of the investigator, the sponsor or any other kind of undue influence. This independent committee should be in conformity with the laws and regulations of the country in which the research experiment is performed. The committee has the right to monitor ongoing trials. The researcher has the obligation to provide monitoring information to the committee, especially any serious adverse events. The researcher should also submit to the committee, for review, information regarding funding, sponsors, institutional affiliations, other potential conflicts of interest and incentives for subjects.
- 14. The research protocol should always contain a statement of the ethical considerations involved and should indicate that there is compliance with the principles enunciated in this Declaration.
- 15. Medical research involving human subjects should be conducted only by scientifically qualified persons and under the supervision of a clinically competent medical person. The responsibility for the human subject must always rest with a medically qualified person and never rest on the subject of the research, even though the subject has given consent.
- 16. Every medical research project involving human subjects should be preceded by careful assessment of predictable risks and burdens in comparison with foreseeable benefits to the subject or to others. This does not preclude the participation of healthy volunteers in medical research. The design of all studies should be publicly available.
- 17. Physicians should abstain from engaging in research projects involving human subjects unless they are confident that the risks involved have been adequately assessed and can be satisfactorily managed. Physicians should cease any investigation if the risks are found to outweigh the potential benefits or if there is conclusive proof of positive and beneficial results.
- 18. Medical research involving human subjects should only be conducted if the importance of the objective outweighs the inherent risks and burdens to the subject. This is especially important when the human subjects are healthy volunteers.
- 19. Medical research is only justified if there is a reasonable likelihood that the populations in which the research is carried out stand to benefit from the results of the research.
- 20. The subjects must be volunteers and informed participants in the research project.
- 21. The right of research subjects to safeguard their integrity must always be respected. Every precaution should be taken to respect the privacy of the subject, the confidentiality of the patient's information and to minimize the impact of the study on the subject's physical and mental integrity and on the personality of the subject.
- 22. In any research on human beings, each potential subject must be adequately informed of the aims, methods, sources of funding, any possible conflicts of interest, institutional affiliations of the researcher, the anticipated benefits and potential risks of the study and the discomfort it may entail.

The subject should be informed of the right to abstain from participation in the study or to withdraw consent to participate at any time without reprisal. After ensuring that the subject has understood the information, the physician should then obtain the subject's freely-given informed consent, preferably in writing. If the consent cannot be obtained in writing, the non-written consent must be formally documented and witnessed.

- 23. When obtaining informed consent for the research project the physician should be particularly cautious if the subject is in a dependent relationship with the physician or may consent under duress. In that case the informed consent should be obtained by a well-informed physician who is not engaged in the investigation and who is completely independent of this relationship.
- 24. For a research subject who is legally incompetent, physically or mentally incapable of giving consent or is a legally incompetent minor, the investigator must obtain informed consent from the legally authorized representative in accordance with applicable law. These groups should not be included in research unless the research is necessary to promote the health of the population represented and this research cannot instead be performed on legally competent persons.
- 25. When a subject deemed legally incompetent, such as a minor child, is able to give assent to decisions about participation in research, the investigator must obtain that assent in addition to the consent of the legally authorized representative.
- 26. Research on individuals from whom it is not possible to obtain consent, including proxy or advance consent, should be done only if the physical/mental condition that prevents obtaining informed consent is a necessary characteristic of the research population. The specific reasons for involving research subjects with a condition that renders them unable to give informed consent should be stated in the experimental protocol for consideration and approval of the review committee. The protocol should state that consent to remain in the research should be obtained as soon as possible from the individual or a legally authorized surrogate.
- 27. Both authors and publishers have ethical obligations. In publication of the results of research, the investigators are obliged to preserve the accuracy of the results. Negative as well as positive results should be published or otherwise publicly available. Sources of funding, institutional affiliations and any possible conflicts of interest should be declared in the publication. Reports of experimentation not in accordance with the principles laid down in this Declaration should not be accepted for publication.

